6.2.2 Statistical considerations

Rate of unacceptable toxicity will be calculated and monitored with the stopping rules based on 2-stage MiniMax design in the table below. For this early stopping rule, we will only include the rate of unacceptable toxicities from the first infusion. Some patients will receive the second planned DLI. If the rate of unacceptable toxicity for the second DLI exceeds these same boundaries as the first infusion, then the protocol will be amended to delete the plan for the second DLI. Toxicity in the other categories will be informally monitored and tabulated by Type and Grade, but they will not be used to determine tolerability of the procedure.

For purposes of toxicity monitoring, each patient will be followed for an unacceptable toxicity for 8 weeks after each NK cell-enriched DLI. Accrual will not be suspended while collecting data for the interim analyses. However, as soon as a boundary within a stage in the table above is crossed, the study will be closed to further accrual.

Patients will be stratified according to T cell depletion usage or not. Analysis within strata is not planned.

Cohort A (7-8/8 HLA-matched related or unrelated transplantation)

A 2-stage MiniMax design will be used to test the null hypothesis that the unacceptable toxicity rate is ≥ 0.40 against the alternative hypothesis that it is ≤ 0.15 in each arm. Seven patients will be treated in the first stage. If the number of patients with an unacceptable toxicity is equal to 3 or more at 16 weeks after the first NK cell enriched-DLI in one arm, then the study for the arm will be terminated. If there are at most 2 patients (29%) with an unacceptable toxicity at 16 weeks after the first NK cell enriched-DLI, the sample size will be increased up to a maximum of 20 patients. If the number of patients who are alive without relapse/progression is equal to 5 or more at 16 weeks after the first NK cell enriched-DLI, then the study for the arm will be terminated. If there are at most 4 patients (20%) with an unacceptable toxicity at 16 weeks after the first NK cell enriched-DLI, this protocol will be deemed safe and continue to accrue to a total of 25 patients. This design has a significance level of 0.05, a power of 0.80, a probability of early termination under the null of 0.58, and an expected sample size under the null of 12 patients.

Table 6

Stage	Total Accrual	Close study/therapy if number of patients with unacceptable toxicity is \geq
1	7	3 (43%)

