2	20	5 (25%)

Cohort B (4-6/8 HLA-matched related transplantation)

A 2-stage MiniMax design will be used to test the null hypothesis that the unacceptable toxicity rate is ≥ 0.45 against the alternative hypothesis that it is ≤ 0.20 in each arm. Nine patients will be treated in the first stage. If the number of patients with an unacceptable toxicity is equal to 4 or more at 16 weeks after the first NK cell enriched-DLI in one arm, then the study for the arm will be terminated. If there are at most 3 patients (33%) with an unacceptable toxicity at 16 weeks after the first NK cell enriched-DLI, the sample size will be increased up to a maximum of 23 patients. If the number of patients who are alive without relapse/progression is equal to 7 or more at 16 weeks after the first NK cell enriched-DLI, then the study for the arm will be terminated. If there are at most 6 patients (26%) with an unacceptable toxicity at 16 weeks after the first NK cell enriched-DLI, this protocol will be deemed safe and continue to accrue to a total of 25 patients. This design has a significance level of 0.05, a power of 0.80, a probability of early termination under the null of 0.64, and an expected sample size under the null of 14 patients.

Table 7

Stage	Total Accrual	Close study/therapy if number of patients with unacceptable toxicity is \geq
1	9	4 (44%)
2	23	7 (30%)

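### The stage-2 toxicity stop in section 6.2.2 counts event-free patients instead of toxicities in both cohorts, so one arm can be both terminated and declared safe

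*Combined protocol and SAP*

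**What the plan says.** Section 6.2.2 opens by making the tables the stopping rule: "Rate of unacceptable toxicity will be calculated and monitored with the stopping rules based on 2-stage MiniMax design in the table below". For Cohort A the hypotheses concern toxicity: "the unacceptable toxicity rate is ≥ 0.40 against the alternative hypothesis that it is ≤ 0.15 in each arm". The plan then states "Seven patients will be treated in the first stage", and the arm stops if 3 or more of them have an unacceptable toxicity. Otherwise it grows to 20 patients.

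At stage 2 two sentences follow each other:

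- The stop sentence reads "If the number of patients who are alive without relapse/progression is equal to 5 or more at 16 weeks" after the first infusion, and the arm is then terminated.
- The next sentence says that with at most 4 patients with an unacceptable toxicity "this protocol will be deemed safe and continue to accrue to a total of 25 patients".

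Table 6 gives the boundaries as 3 of 7 and 5 of 20. Its column is headed "Close study/therapy if number of patients with unacceptable toxicity is" at or above the listed number.

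Cohort B has the same structure, with 9 patients in stage 1, 23 in stage 2, and null and alternative toxicity rates of 0.45 and 0.20. Its stop sentence reads "If the number of patients who are alive without relapse/progression is equal to 7 or more at 16 weeks". The sentence after it declares the arm safe with at most 6 toxicities. Table 7 gives 4 of 9 and 7 of 23, again as counts of unacceptable toxicity.

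**The concern.** The stage-2 stop sentence takes the toxicity cut-offs from Tables 6 and 7 (5 and 7) and applies them to patients who are alive without relapse or progression (event-free, below). That is a favourable outcome, so the sentence ends an arm when enough patients do well. This has two consequences.

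- **Opposite verdicts.** An arm with few toxicities and a reasonable number of event-free patients is terminated by one sentence and declared safe by the next.
- **A gap in the unsafe direction.** An arm with 5 or more toxicities (A) or 7 or more (B), but fewer event-free patients than the cut-off, meets neither stage-2 sentence. Only the table stops it.

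This is the written decision rule for a primary safety endpoint, and it applies to each arm of both cohorts. The wording matches the PFS rule in section 6.1.2, so a drafting carry-over is likely, although the documents do not say so.

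**Working it through.** **1. What each element of section 6.2.2 counts**

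| Element | Cohort A | Cohort B | Variable counted |
|---|---|---|---|
| Hypotheses | 0.40 vs 0.15 | 0.45 vs 0.20 | toxicity |
| Stage-1 stop | ≥3 of 7 | ≥4 of 9 | toxicity |
| Stage-2 stop, table | ≥5 of 20 | ≥7 of 23 | toxicity |
| Stage-2 stop, text | ≥5 | ≥7 | event-free patients |
| Declared safe | ≤4 of 20 | ≤6 of 23 | toxicity |

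Only the stage-2 stop in the text differs.

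**2. Do the stated properties fit a toxicity count?**

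Let X1 be the toxicities among the first n1 patients and X2 those among the remaining n − n1. The arm is declared safe if X1 ≤ a1 and X1 + X2 ≤ a. Then

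P(safe | p) = Σ P(X1 = x) · P(X2 ≤ a − x), for x = 0 to a1

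PET (probability of early termination) = 1 − P(X1 ≤ a1)

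EN (expected sample size) = n1 + (n − n1)(1 − PET)

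Cohort A (n1 = 7, a1 = 2, n = 20, a = 4):

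- At p = 0.40: 0.02799×0.35304 + 0.13064×0.16858 + 0.26127×0.05790 = 0.0470 (significance level).
- At p = 0.15: 0.30962 + 0.34928 + 0.14507 = 0.8040 (power).
- PET at 0.40 = 1 − (0.02799 + 0.13064 + 0.26127) = 0.5801. EN = 7 + 13×0.4199 = 12.46.

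Cohort B (n1 = 9, a1 = 3, n = 23, a = 6):

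- At p = 0.45: 0.00252 + 0.01144 + 0.01856 + 0.01339 = 0.0459.
- At p = 0.20: 0.13266 + 0.28875 + 0.26278 + 0.12299 = 0.8072.
- PET at 0.45 = 0.6386. EN = 9 + 14×0.3614 = 14.06.

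The plan states 0.05, 0.80, 0.58 and 12 for Cohort A, and 0.05, 0.80, 0.64 and 14 for Cohort B. Both sets agree. A minimax search at significance level 0.05 and power 0.80 returns exactly these designs. The properties therefore belong to a rule that counts toxicities at both stages.

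**3. The contradiction without any assumption**

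Take a Cohort A arm with 2 toxicities and 15 event-free patients among 20 at 16 weeks. Since 15 ≥ 5, the stop sentence terminates it. Since 2 ≤ 4, the next sentence declares it safe.

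**4. How often the stop sentence would be met if read literally**

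The documents give no 16-week PFS rate, so a range for that rate, q, is assumed:

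- Upper value: constant hazard from the one-year null rates in section 6.1.2, so 0.46^(16/52) = 0.787 (A) and 0.34^(16/52) = 0.718 (B). Those one-year rates come from the transplant series in section 2.3, while the 16 weeks here run from the first infusion.
- Middle value: 0.50.
- Low value: the one-year nulls themselves, 0.46 and 0.34.

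T = P(event-free ≥ 5 of 20) in A, or P(event-free ≥ 7 of 23) in B. S is the probability of being declared safe at the acceptable toxicity rate (0.8040 in A, 0.8072 in B). Toxicity and PFS may be correlated, so the probability of both verdicts is bounded by max(0, S + T − 1) and min(S, T).

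| Cohort | q | T | Both verdicts |
|---|---|---|---|
| A | 0.787 | >0.9999 | 0.804 |
| A | 0.50 | 0.994 | 0.798 to 0.804 |
| A | 0.46 | 0.985 | 0.789 to 0.804 |
| B | 0.718 | >0.9999 | 0.807 |
| B | 0.50 | 0.983 | 0.790 to 0.807 |
| B | 0.34 | 0.713 | 0.521 to 0.713 |

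For the last row the lower bound is 0.8072 + 0.7134 − 1 = 0.521. Under independence it would be 0.8072 × 0.7134 = 0.576.

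**The case against.** The strongest reply is that this is a drafting slip that misleads nobody. The opening sentence of 6.2.2 names the table as the stopping rule, and every other element of the section fits only a toxicity count. A monitoring group holding Table 6 is unlikely to close an arm because its patients are doing well. After stage 2 at most 25 − 20 = 5 patients per arm (A) or 25 − 23 = 2 (B) remain to be accrued, and fewer still if accrual runs on during the 16-week follow-up. The probabilities above describe a literal reading under an assumed PFS; they are not the chance that the trial goes wrong.

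Most of this stands. The intended rule can be recovered, little accrual is at risk, and the point does not depend on the probabilities, since the example in step 3 needs no assumption. But nothing in 6.2.2 ranks the tables above the text. The other sentence that points to a table, "as soon as a boundary within a stage in the table above is crossed", is not a clean cross-reference either: Tables 6 and 7 come after it, and the nearest table before it is Table 5, which concerns PFS. Recoverability lowers the risk of a wrong decision but leaves two opposite written instructions for a primary safety endpoint.

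**Conclusion.** The concern holds. In both cohorts the stage-2 stop sentence for unacceptable toxicity counts the wrong variable. It contradicts Table 6 or Table 7 and the sentence that follows it. This is an internal inconsistency; the two-stage design is correctly calculated. For an arm at the acceptable toxicity rate, both verdicts would apply with probability 0.79 to 0.80 in Cohort A across the assumed PFS range. In Cohort B the figure is 0.79 to 0.81 at 16-week PFS of 0.50 or 0.718, and 0.52 to 0.71 at 0.34. These figures assume a literal reading and a 16-week PFS that the documents do not give; they do not assume independence of toxicity and PFS. What is exposed is mainly the terminate-or-safe verdict itself. It must be corrected because it is the written rule for a primary safety endpoint and appears twice.

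**What to change.** Reconcile the stage-2 stop sentence for each cohort in section 6.2.2 with Tables 6 and 7, by replacing the reference to event-free patients with a reference to patients with an unacceptable toxicity. In the same edit, the pointer to a table above could name Tables 6 and 7. The cost is one phrase in each of two sentences, made by protocol amendment. Boundaries, sample sizes and operating characteristics stay as they are.

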6.3 Secondary Objectives

1. To evaluate the recovery of immune cell populations pre and post infusion in patients receiving NK cell-enriched DLI administered alone or administered with TLR9 ligand, DUK-CPG-001.
2. To evaluate the immune function with antigen specific recovery with Elispot, Immunoscope, and flow-cytometric cytokine assay, and functional NK lysis assay, pre and post infusion in patients receiving NK cell-enriched DLI administered alone or administered with TLR9 ligand, DUK-CPG-001.

The repeated measurements of immune cell numbers and immune function will be plotted against time for each patient. The means of the measurements across patients will be calculated with their 95% confidence intervals. These means will also be plotted against time to show the change with time. The generalized estimating equation method will be used to estimate the rates of change of the mean cell numbers and mean immune function over time, along with their 95% confidence intervals.

6.31 Secondary objectives 1 and 2:

Evaluation of the recovery of immune cell populations pre and post infusion will be performed.

Immunophenotype

NK cell: CD3-CD56^{bright}CD16-, CD3-CD56^{bright}CD16+, CD3-CD56^{dim}CD16+

CD3+ T cell: CD3+

CD4+ T cell: CD3+CD4+

CD8+ T cell: CD3+CD8+

$\gamma\delta$ T cells: CD3+ $\gamma\delta$ TCR+

B cell: CD19+, CD3-, CD16-, CD56-

Regulatory T cell: CD4+, CD25+, CD62L+

Cytotoxic T cell: CD8+, CD57+, CD28-

Activated T cell: CD8+, HLA-DR+

Recent thymic emigrants: CD4+, CD45RA+/CD45RO-, CD62L+

Plasmacytoid dendritic cell: CD123+, CD11c-

Myeloid dendritic cell: CD123-, CD11c+

NKT cell: CD3+, CD16+/CD56+

Quantification of these lymphoid subsets were performed by flow cytometry on fresh peripheral blood prior to, and then at 1 day, and 1 month after each NK cell enriched DLI and at 3, 6, and 12 months following the last NK enriched DLI.^{87,88} The median number of these cell populations will be tabulated at each time points. A plot of number of these against time point will be drawn, using a separate line for each patient.

Evaluation of the immune function with antigen specific recovery with Elispot, Immunoscope, and flow-cytometric cytokine assay, and functional NK lysis assay, pre and post infusion will be performed prior to, and then at 1 day, and 1 month after each NK cell enriched DLI, and at 3, 6, and 12 months following the last NK enriched DLI. The median number will be tabulated at each time points. A plot of number of these against time point will be drawn, using a separate line for each patient.

Analysis of the Microbiota: Shannon diversity index will be compared using unpaired two-sided Student's *t* tests with a more stringent cut-off of 0.0125 given multiple comparisons, by the Bonferroni correction for 4 time periods of independent comparisons. Comparisons of bacterial populations will be made by using the Adonis non-parametric method from within the Qiime package using Unifrac distance matrices from the populations being compared. P values will be calculated with $\alpha = 0.05$. Metastats will be used for further statistical analyses of population structure, membership, and diversity with metadata such as time from transplant and dietary measurements such as caloric intake ⁹⁴. Changes in specific bacterial families of interest will be compared using a two-sided Student's *t* test, with normality confirmed by D'Agostino and Pearson omnibus test with $p \leq 0.05$. All other comparisons will be done using two-sided Mann-Whitney tests. The R packages vegan⁹⁵, phyloseq⁹⁶, APE⁹⁷, randomForest⁹⁸, and arules⁹⁹ will be used for identification of associative patterns between taxa most associated with GVHD and disease responses.

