2. To evaluate the one-year progression-free survival rates in patients receiving NK cell-enriched DLI administered with a Toll-like receptor 9 (TLR9) ligand, DUK-CPG-001, from a 7-8/8 HLA-matched related or unrelated donor or 4-6/8 HLA-matched related donor following allogeneic stem cell transplantation
3. To evaluate the rates of unacceptable toxicity of using NK cell-enriched DLI administered alone from a 7-8/8 HLA-matched related or unrelated donor or 4-6/8 HLA-matched related donor following allogeneic stem cell transplantation.
4. To evaluate the rates of unacceptable toxicity of using NK cell-enriched DLI administered with TLR9 ligand, DUK-CPG-001, from a 7-8/8 HLA-matched related or unrelated donor or 4-6/8 HLA-matched related donor following allogeneic stem cell transplantation.

The secondary objectives of this study are:

1. To evaluate the recovery of immune cell populations pre and post infusion in patients receiving NK cell-enriched DLI administered alone or administered with TLR9 ligand, DUK-CPG-001.
2. To evaluate the immune function with antigen specific recovery with Elispot, Immunoscope, and flow-cytometric cytokine assay, and functional NK lysis assay, pre and post infusion in patients receiving NK cell-enriched DLI administered alone or administered with TLR9 ligand, DUK-CPG-001.

Patient population

Patients who have undergone an allogeneic transplantation, using a 7-8/8 HLA-matched related/unrelated donor (Cohort A) or 4-6/8 HLA-matched related donor (Cohort B). Specific inclusion and exclusion criteria are detailed in 3.0 Eligibility criteria.

Number of patients

A total of 50 patients (25 patients in each arm) will be enrolled in Cohort A, and 50 patients (25 patients in each arm) will be enrolled in Cohort B.

Study design and methodology

This is a randomized, parallel phase II study to evaluate the rates of progression-free survival and unacceptable toxicity in patients receiving NK cell-enriched DLIs when administered alone or administered with the TLR9 agonist, DUK-CPG-001, from a 7-8/8 HLA-matched related/unrelated donor (Cohort A) or 4-6/8 HLA-matched related donor (Cohort B) following allogeneic stem cell transplantation. Randomization will be stratified for disease types (myeloid versus lymphoid malignancies). Primary endpoints are analyzed separately in Cohort A and B.

Cohort A: 8/8 HLA-matched (related or unrelated) donor
("NK cell enriched-DLI only" arm or "NK cell enriched-DLI + DUK-CPG-001" arm)

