4. TREATMENT PLAN

4.1 Patient prior to starting therapy

Within 21 days prior to the 1st NK DLI, patients will be screened as follow:

- An updated medical history will be collected
- A physical examination performed including a pregnancy test, if the patient is a female of childbearing potential.
- Labs:
 - CBC (with differential preferred),
 - creatinine,
 - AST, ALT, and total bilirubin,
 - calcium,
 - LDH,
 - potassium,
 - sodium,
 - bicarbonate,
 - chloride and glucose,
 - albumin,
 - phosphorous,
 - magnesium and
 - alkaline phosphatase
 - Immune reconstitution panel
- Patients will have blood or marrow stored for chimerism analysis.
- Research blood samples for analysis of immune function.
- Stool will be collected for analysis of microbiota
- Tests documenting the patient's disease state:
- Bone marrow aspirate and biopsy for patients with known abnormalities of the marrow previous to the transplant should have tests repeated to check for the prior abnormalities such as morphology, flow cytometry, PCR, or cytogenetics.
 - Blood studies, and/or
 - Radiographic tests such as CTs, MRI, PET scans as determined by treating physician, for standardized response evaluations as outlined in section 4.3.2).

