The tests and procedures are not in addition or in excess of our standards for allogeneic transplants outside of this protocol. The transplant team is available for constant communication with the patients and their local physicians to monitor their toxicities. Further follow up at the transplant center will be required as needed if the patient has a toxicity due the transplant or infusion procedures. Patients with a grade 3 or greater toxicity

due to the study will be seen every other week at a minimum until the toxicity is < grade 3, and then will be seen as clinically appropriate.

NOTE: If a patient does not receive the 2nd DLI, they will be followed every 3 months after their 1st DLI.

4.3.4 Stool Collection and Microbiome Analysis:

We will collect stool samples from patients at the following time points throughout the study: pre-DLI, 1 month post, pre-second DLI, 1 month post, then at 3, 6 and 12 months after last DLI for one year. Stool samples from patients may be stored at 4°C for up to 24 h before freezing at -80°C for batch analysis. Samples not used during this research will be stored in the Duke Data and Specimen Repository (IRB Pro00006268) unless the patient does not consent to the Repository. If no consent to store the samples is obtained, the samples will be destroyed after study analyses are complete.

To analyze the gut microbiome, DNA will be extracted from fecal samples⁹¹ and gut flora bacterial density will be quantified using real-time quantitative polymerase chain reaction (qPCR) as described.⁹² We will amplify 16S ribosomal RNA (rRNA) using Illumina HiSeq platform and analyze the data using the Qiime script package with parallel processing.⁹³ Sequences will be de-noised and clustered at 97% identity using USEARCH and aligned to the 16S rRNA gene, using the align.seqs.py wrapper with the PyNAST algorithm and Greengenes reference alignment. Based on these results, we will calculate diversity (Shannon Diversity, primary endpoint, and Chao1) and construct phylogenetic trees using computational analysis software.

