6.0 STUDY DESIGN AND ANALYSIS

This is a randomized, parallel phase II study of NK cell-enriched DLIs when administered alone or administered with the TLR9 agonist, DUK-CPG-001, from a 7-8/8 HLA-matched related/unrelated donor (Cohort A) or 4-6/8 HLA-matched related donor (Cohort B) following allogeneic stem cell transplantation.

In Cohort A, a total of 50 patients will be randomized with equal allocation to two arms defined by whether or not a TLR9 ligand, DUK-CPG-001, is administered with NK cell-enriched DLIs. In Cohort B, a total of 50 patients will be randomized with equal allocation to the two arms. Stratification will be done within disease types (myeloid or lymphoid diseases) in each cohort. A block randomized design is used to randomize patients to the two treatments within each stratum for each cohort. Primary endpoints are analyzed separately in Cohort A and B.

6.1 Primary Objectives 1 and 2

1. To evaluate the one-year progression-free survival rates in patients receiving NK cell-enriched DLI administered alone from a 4-6/8 HLA-matched related or 7-8/8 HLA-matched donor following allogeneic stem cell transplantation.
2. To evaluate the one-year progression-free survival rates in patients receiving NK cell-enriched DLI administered with a TLR9 ligand, DUK-CPG-001, from a 4-6/8 HLA-matched related or 7-8/8 HLA-matched donor following allogeneic stem cell transplantation

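### The Shannon diversity t tests use neither the planned pre-DLI stool value nor the randomisation stratum; where the randomised arms are compared, a linear model with both would gain power at little cost

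*Combined protocol and SAP*

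**What the plan says.** Section 4.3.4 (Stool Collection and Microbiome Analysis) ranks the diversity measures: "we will calculate diversity (Shannon Diversity, primary endpoint, and Chao1". It sets the sampling times as "pre-DLI, 1 month post, pre-second DLI, 1 month post, then at 3, 6 and 12 months after last DLI for one year", which is up to seven samples when two DLIs are given. The baseline sample also appears in the screening list of Section 4.1 ("Stool will be collected for analysis of microbiota") and in the first Pre column of Table 9, Appendix V.

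Section 6.0 gives the design: "In Cohort A, a total of 50 patients will be randomized with equal allocation to two arms", and the same for Cohort B. On strata it says: "Stratification will be done within disease types (myeloid or lymphoid diseases) in each cohort".

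The microbiota paragraph of Section 6.31 names the method, a t test: "Shannon diversity index will be compared using unpaired two-sided Student's". For the significance level, the same sentence sets a corrected threshold: "with a more stringent cut-off of 0.0125 given multiple comparisons, by the Bonferroni correction for 4 time periods of independent comparisons". It states no baseline covariate, pairing, repeated-measures model or stratum term for Shannon diversity. It does not say which groups are compared or which four of the sampling times are meant.

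Other parts of the plan do use earlier values. Section 6.3 applies generalized estimating equations to immune cell numbers and immune function. Section 6.3.1.1 defines the NK response as a percent increase over the pre-DLI level. The microbiota paragraph speaks of changes for bacterial families.

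**The concern.** Patients may enter one to six months after transplant, with myeloid or lymphoid disease and differing immunosuppression, so their diversity before the DLI is likely to vary. An unpaired t test of a post-DLI value leaves all of that variation in the error term. If the randomised arms are compared, the pre-DLI value is measured before treatment, and adjusting for it removes predictable noise and chance imbalance without biasing the arm effect. The stratum was used to randomise and belongs in the model for the same reason.

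What is at stake is efficiency. A t test on independent groups is valid, but with small arms and a per-test level of 0.0125 it detects only large differences, and the information that could sharpen it is already due to be collected.

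**Working it through.** **Inputs from the plan.** Two-sided test at 0.0125 (Section 6.31). At most 25 per arm in each cohort: "A total of 50 patients (25 patients in each arm) will be enrolled in Cohort A", and likewise for Cohort B (Protocol Summary; Section 6.0). A pre-DLI sample is planned for every patient.

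**Inputs assumed, because the plan gives none.** Standardised difference d = 0.80 SD at a post-DLI visit; pre/post correlation ρ = 0.3, 0.5 or 0.7; complete samples.

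**1. The plan's own figure.** 0.05/4 = 0.0125, which agrees. With four independent tests the familywise error is 1 − (1 − 0.0125)⁴ = 0.049. The level can stay.

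**2. Unpaired t test, n = 25 per arm.** Noncentrality = d√(n/2) = 0.80 × √12.5 = 2.828. With 48 df the critical value is 2.595, and power is 59.4%. For 80% power the test needs d of about 0.98 SD. With the cohorts pooled (50 per arm) it needs 0.68 SD.

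**3. Linear model with the pre-DLI value.** The residual SD is multiplied by √(1 − ρ²), so the noncentrality is 2.828/√(1 − ρ²), with 47 df and critical value 2.597.

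| ρ | Variance removed (ρ²) | Noncentrality | Power |
|---|---|---|---|
| 0.3 | 9% | 2.965 | 64.4% |
| 0.5 | 25% | 3.266 | 74.5% |
| 0.7 | 49% | 3.961 | 90.8% |

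An effect with exactly 60% unadjusted power (d = 0.804) reaches 65%, 75% and 91%.

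**4. Cost if the baseline is uninformative (ρ = 0).** Spending two degrees of freedom (baseline and stratum) takes power from 59.4% to 59.3%, a loss under 0.2 points. That counts degrees of freedom only. Chance imbalance in the covariate also inflates the variance of the arm effect, on average by 1 + 1/(2n − 4) = 1 + 1/46 = 1.022. The noncentrality becomes 2.828/√1.022 = 2.798 and power about 58%. The full cost at zero correlation is therefore a little over one point. The same factor takes about one point off each row of the table. A simulation of 4,000 trials per setting, fitting the baseline-adjusted model, agrees: 63.8%, 73.6% and 89.4%.

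**5. Why not a change score.** Its SD is multiplied by √(2(1 − ρ)), which is 1.183, 1.000 and 0.775. At d = 0.80 its power is 43%, 59% and 85%: worse than the plain t test at ρ = 0.3, equal at 0.5, and below the linear model throughout. The ratio of change-score variance to model variance is 2(1 − ρ)/(1 − ρ²) = 2/(1 + ρ), or 1.54, 1.33 and 1.18, so the difference matters most at low correlation.

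**6. Fewer samples.** With 15 per arm, d = 0.80 has 33% power unadjusted, and 37%, 45% or 65% adjusted (formula of step 3).

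**The case against.** The strongest objection is that the plan never says this is a comparison of arms. Section 2.5 gives the purpose of the stool work as relating the gut environment to GVHD, and the microbiota paragraph ends with taxa associated with GVHD and disease response. If the t tests compare patients with and without GVHD, the groups are not randomised. Adjustment is then not automatically free of bias, a missing-baseline indicator is not safe in general, and 25 against 25 is the wrong split. Pre-DLI diversity might itself be the predictor of interest, so adjusting for it could change the question. This stands, and it limits the point to arm comparisons. If the intended comparison is instead before against after within patients, an unpaired test is mis-specified. Either way the groups must be named.

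The size is also uncertain. The 12-month sample falls about 13 to 15 months after the first DLI when two are given (12 months plus the one to three months between infusions), and correlation with the pre-DLI value is likely to be lower by then. Arms may stop at 9 or 12 patients (Section 6.1.2), and deaths will thin late visits. Conversely, Section 6.0 requires separate cohort analysis only for the primary endpoints, so pooling is open and would reduce the detectable difference. All of this stands.

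A reader might infer that bacterial families share the fault. The documents do not support that. If changes there means post-minus-pre scores compared between arms, those scores already use the baseline, and the linear model is at least as efficient, mainly at low correlation. The paragraph does not confirm that per-patient scores are meant.

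**Conclusion.** The point holds as a conditional, minor efficiency gain. The planned Shannon tests use neither the pre-DLI value nor the stratum. Where randomised arms are compared, a linear model with both should replace them. At 25 complete patients per arm and 0.80 SD, the gain is about 5, 15 or 31 points of power at correlations of 0.3, 0.5 or 0.7, less about one point for chance baseline imbalance. It is likely to be smaller at late visits. The correlations, the effect size and complete sampling are all assumptions.

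Two stronger readings should be resisted. One is that baseline adjustment is right for every Shannon comparison in the plan; the groups are unnamed, and for GVHD or response groups it should not be imposed by default. The other is that the word primary in Section 4.3.4 makes this a threat to the trial's main results. There it ranks Shannon diversity above Chao1 within the microbiome work. Microbiota appear in none of the four primary or two secondary objectives, no power is claimed for the test, and the PFS and toxicity conclusions are unaffected.

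**What to change.** In the microbiota paragraph of Section 6.31:

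- Name the groups compared and the four time periods.
- Where post-DLI Shannon diversity is compared between the randomised arms, replace the t test at each post-DLI period with a linear model on arm, pre-first-DLI Shannon diversity and disease-type stratum, tested at 0.0125. Keep patients without a pre-DLI sample by means of a missing-baseline indicator.
- For comparisons by GVHD or response status, state the question first and decide on baseline adjustment from it.
- Say what changes in bacterial families means. If it means post-minus-pre scores between arms, the same linear model may be used in place of the change score.

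The cost is a few sentences of text, one or two degrees of freedom per model, and one more if the missing-baseline indicator is needed. No new samples, visits or patients are required.

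### Bacterial-family comparisons: the normality criterion attached to the t test is reversed, because an omnibus p ≤ 0.05 rejects normality

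*Combined protocol and SAP*

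**What the plan says.** The rule is in the paragraph on analysis of the microbiota in section 6.31 of the combined protocol and SAP. For bacterial families: "Changes in specific bacterial families of interest will be compared using a two-sided Student's *t* test", and then "with normality confirmed by D'Agostino and Pearson omnibus test with" p ≤ 0.05. The next sentence is "All other comparisons will be done using two-sided Mann-Whitney tests".

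The same paragraph opens with a separate rule for diversity: "Shannon diversity index will be compared using unpaired two-sided Student's *t* tests with a more stringent cut-off of 0.0125". That rule carries no normality condition.

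No other section restates or corrects the family rule. The families of interest and the groups to be compared are not named, and no significance level is clearly attached to the family comparison.

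**The concern.** A t test with a normality check is meant to be used when the data look normal. The criterion as printed admits the t test when the check has rejected normality. An analyst who follows the text literally would keep the t test for data that violate its assumption.

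At stake are the power of the family comparisons, since bacterial abundances may well be skewed, and the clarity of a prespecified rule. With no more than 25 patients per arm in a cohort, there is little power to give away.

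**Working it through.** **1. Direction of the test.** D'Agostino-Pearson omnibus test: the null hypothesis is that the data are normal. Hence p ≤ 0.05 rejects normality, and only p > 0.05 is compatible with it. The plan attaches p ≤ 0.05 to confirming normality. The reversal follows from this alone and needs no simulation.

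**2. The plan's own figures.** The plan states no power or sample size for this rule, so there is none to reproduce. The one figure in the paragraph that can be checked is the Bonferroni cut-off for Shannon diversity: 0.05 / 4 = 0.0125, as stated.

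**3. How often the printed criterion is met.** The sample sizes follow the protocol summary ("A total of 50 patients (25 patients in each arm) will be enrolled in Cohort A"). The distribution shapes are assumptions. 20,000 simulated samples per row; share with omnibus p ≤ 0.05:

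| Shape | n = 25 | n = 50 | Both of two samples, n = 25 |
|---|---|---|---|
| Normal | 0.061 | 0.058 | 0.003 |
| Lognormal, log-SD 1 | 0.884 | 0.997 | 0.779 |
| Exponential | 0.701 | 0.962 | 0.492 |

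Normal data meet the printed criterion about 6% of the time; lognormal data meet it about 88% of the time at n = 25. With the inequality corrected, normal samples would go to the t test in 1 − 0.061 = 0.939, about 94%.

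**4. What the two readings of the Mann-Whitney sentence imply.**
- *Fallback reading* (families that do not meet the criterion): skewed families go to the t test, normal-looking families to Mann-Whitney.
- *Other-variables reading*: the criterion is still reversed, and the plan names no test for families that fail the check.

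**5. Power on the fallback reading.** Assumptions: 25 per arm, lognormal data, two-sided 0.05 for both the omnibus test and the comparison, 4,000 replicates per scenario, t test triggered as written when either arm rejects normality.

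| Log-SD | Log-shift | As written | Corrected | Loss |
|---|---|---|---|---|
| 1.5 | 1.0 | 0.32 | 0.62 | 0.30 |
| 1.0 | 0.7 | 0.50 | 0.66 | 0.16 |
| 0.5 | 0.35 | 0.63 | 0.67 | 0.04 |
| 0.3 | 0.2 | 0.60 | 0.63 | 0.03 |

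The Monte Carlo standard error is at most √(0.5 × 0.5 / 4,000) ≈ 0.008, so the second decimal is approximate.

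**6. Sensitivity.**
- *Combining the arms.* The plan does not say how. If either arm rejecting is enough, the t test is chosen in 99.9% (log-SD 1.5) and 98.8% (log-SD 1.0) of datasets. If both must reject, the shares are about 94.5% and 77%, and power as written is 0.33 and 0.51, nearly unchanged.
- *Changes rather than levels.* The plan analyses changes. For simulated post-minus-pre differences, power as written against corrected is 0.22 against 0.37 (log-SD 1.5) and 0.35 against 0.42 (log-SD 1.0). At log-SD 0.5, with an assumed correlation of 0.5, it is about 0.66 against 0.68.
- *Type I error.* Rejection under the null, as written, is 0.03 to 0.04.

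**The case against.** The best defence is that this is a drafting slip. The words about confirming normality show the intent, and p ≤ 0.05 may be the level of the omnibus test, or the level of the comparison itself, put in the wrong place. An analyst might well do the sensible thing. This is plausible, but the sentence ties the inequality to confirming normality. If the figure was meant only as a level, the plan still does not say which result leads to which test, and the same edit is needed.

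Three stronger readings are tempting, and the documents do not support them:

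- *That the plan expressly sends normal-looking families to Mann-Whitney.* It does not say so. After sentences on diversity, population structure and families, the reference to all other comparisons may mean other variables. The fallback is the natural reading but not the only one.
- *That the rule costs substantial power in nearly every comparison.* The plan gives no abundance distribution. The loss is large only under strong assumed skew and shrinks to 0.03 to 0.04 under mild skew.
- *That trial conclusions or false-positive rates are at risk.* Type I error is not raised. Microbiota analysis is in neither the primary objectives nor the two listed secondary objectives, and Shannon diversity, which section 4.3.4 labels the primary endpoint of the microbiome analysis, has no normality condition.

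What stands of the objection is the limit on size and importance. The reversed inequality itself is not answered.

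**Conclusion.** The criterion is wrong as written: an omnibus p ≤ 0.05 cannot confirm normality. This conclusion rests only on the null hypothesis of the named test.

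The consequence depends on how the Mann-Whitney sentence is read. As a fallback, it reverses the allocation of tests, at a power cost between 0.03 and 0.30 over the four assumed lognormal scenarios with 25 per arm. If it refers to other variables, those power figures do not apply, and the defect is a reversed criterion with no stated test for families that fail it.

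Severity is low. The family comparisons are exploratory, and the decision rules for progression-free survival (section 6.1.2) and unacceptable toxicity (section 6.2.2) do not use them.

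**What to change.** Amend the sentence in section 6.31 to say that each family is compared by two-sided t test only if the omnibus test gives p > 0.05, and by two-sided Mann-Whitney test otherwise. Say whether both groups must pass the check. State the significance level of the family comparison separately from that of the omnibus test, and make clear which analyses the sentence on all other comparisons covers.

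An optional alternative is to drop the pre-test and use Mann-Whitney for every family. This is simpler, but it is a preference and is not needed to remove the error.

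Either edit is confined to the wording of this paragraph and costs nothing: no patient, sample, visit or other analysis changes.
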